5.6 Rescue Medications & Supportive Care

5.6.1 Supportive Care Guidelines

Subjects should receive appropriate supportive care measures as deemed necessary by the treating investigator. Suggested supportive care measures for the management of adverse events with potential immunologic etiology are outlined below. Where appropriate, these guidelines include the use of oral or intravenous treatment with corticosteroids as well as additional anti-inflammatory agents if symptoms do not improve with administration of corticosteroids. Note that several courses of steroid tapering may be necessary as symptoms may worsen when the steroid dose is decreased. For each disorder, attempts should be made to rule out other causes such as metastatic disease or bacterial or viral infection, which might require additional supportive care. The treatment guidelines are intended to be applied when the investigator determines the events to be related to pembrolizumab.

Note: if after the evaluation the event is determined not to be related, the investigator does not need to follow the treatment guidance (as outlined below). Refer to Section 5.2.1 for dose modification.

It may be necessary to perform conditional procedures such as bronchoscopy, endoscopy, or skin photography as part of evaluation of the event.

- **Pneumonitis:**
 - For **Grade 2 events**, treat with systemic corticosteroids. When symptoms improve to Grade 1 or less, steroid taper should be started and continued over no less than 4 weeks.
 - For **Grade 3-4 events**, immediately treat with intravenous steroids. Administer additional anti-inflammatory measures, as needed.
 - Add prophylactic antibiotics for opportunistic infections in the case of prolonged steroid administration.
- **Diarrhea/Colitis:**

Both afatinib and MK-3475 can cause diarrhea. Subjects should additionally be carefully monitored for signs and symptoms of enterocolitis (such as diarrhea, abdominal pain, blood or mucus in stool, with or without fever) and of bowel perforation (such as peritoneal signs and ileus).

 - All subjects who experience diarrhea/colitis should be advised to drink liberal quantities of clear fluids. If sufficient oral fluid intake is not feasible, fluid and electrolytes should be substituted via IV infusion. For Grade 2 or higher diarrhea, consider GI consultation and endoscopy to confirm or rule out colitis. Diarrhea

should be managed aggressively with anti-diarrheal agents such as: loperamide, diphenoxylate/atropine and tincture of opium if necessary. For **Grade 2 diarrhea/colitis** that persists greater than 3 days, administer oral corticosteroids.

- For **Grade 3 or 4 diarrhea/colitis** that persists > 1 week, treat with intravenous steroids followed by high dose oral steroids.
- When symptoms improve to Grade 1 or less, steroid taper should be started and continued over no less than 4 weeks.

- **Management of Acneiform Rash** – Afatinib as with other EGFR-inhibitors can cause a classic acneiform rash. Acneiform rash attributed to afatinib \geq grade 2 should be managed aggressively with cleocin solution and appropriate anti-biotics such as doxycycline. Management for grade 1 acneiform rash per investigator's discretion.
- **Type 1 diabetes mellitus (if new onset, including diabetic ketoacidosis [DKA]) or \geq Grade 3 Hyperglycemia, if associated with ketosis (ketonuria) or metabolic acidosis (DKA)**
 - For T1DM or Grade 3-4 Hyperglycemia
 - Insulin replacement therapy is recommended for Type I diabetes mellitus and for Grade 3-4 hyperglycemia associated with metabolic acidosis or ketonuria.
 - Evaluate patients with serum glucose and a metabolic panel, urine ketones, glycosylated hemoglobin, and C-peptide.
- **Hypophysitis:**
 - For Grade 2 events, treat with corticosteroids. When symptoms improve to Grade 1 or less, steroid taper should be started and continued over no less than 4 weeks. Replacement of appropriate hormones may be required as the steroid dose is tapered.
 - For Grade 3-4 events, treat with an initial dose of IV corticosteroids followed by oral corticosteroids. When symptoms improve to Grade 1 or less, steroid taper should be started and continued over no less than 4 weeks. Replacement of appropriate hormones may be required as the steroid dose is tapered.
- **Hyperthyroidism or Hypothyroidism:**

Thyroid disorders can occur at any time during treatment. Monitor patients for changes in thyroid function (at the start of treatment, periodically during treatment, and as indicated based on clinical evaluation) and for clinical signs and symptoms of thyroid disorders.

 - Grade 2 hyperthyroidism events (and Grade 2-4 hypothyroidism):
 - In hyperthyroidism, non-selective beta-blockers (e.g., propranolol) are suggested as initial therapy.
 - In hypothyroidism, thyroid hormone replacement therapy, with levothyroxine or liothyroinine, is indicated per standard of care.
 - Grade 3-4 hyperthyroidism
 - Treat with an initial dose of IV corticosteroid followed by oral corticosteroids. When symptoms improve to Grade 1 or less, steroid taper should be started and continued over no less than 4 weeks. Replacement of appropriate hormones may be required as the steroid dose is tapered.

- **Hepatic:**
 - For Grade 2 events, monitor liver function tests more frequently until returned to baseline values (consider weekly).
 - Treat with IV or oral corticosteroids
 - For Grade 3-4 events, treat with intravenous corticosteroids for 24 to 48 hours.
 - When symptoms improve to Grade 1 or less, a steroid taper should be started and continued over no less than 4 weeks.
- **Renal Failure or Nephritis:**
 - For Grade 2 events, treat with corticosteroids.
 - For Grade 3-4 events, treat with systemic corticosteroids.
 - When symptoms improve to Grade 1 or less, steroid taper should be started and continued over no less than 4 weeks.
- **Management of Infusion Reactions:**

Signs and symptoms usually develop during or shortly after drug infusion and generally resolve completely within 24 hours of completion of infusion.

Table 7 shows treatment guidelines for subjects who experience an infusion reaction associated with administration of MK-3475. Please also see Events of Clinical Interest Appendix attached at end of protocol for further details.

Table 7. Infusion Reaction Treatment Guidelines

NCI CTCAE Grade	Treatment	Premedication at Subsequent Dosing
Grade 1 Mild reaction; infusion interruption not indicated; intervention not indicated	Increase monitoring of vital signs as medically indicated until the subject is deemed medically stable in the opinion of the investigator.	None
Grade 2 Requires infusion interruption but responds promptly to symptomatic treatment (e.g., antihistamines, NSAIDS, narcotics, IV fluids); prophylactic medications indicated for <=24 hrs	Stop Infusion and monitor symptoms. Additional appropriate medical therapy may include but is not limited to: IV fluids Antihistamines NSAIDS Acetaminophen Narcotics Increase monitoring of vital signs as medically indicated until the subject is deemed medically stable in the opinion of the investigator. If symptoms resolve within one hour of stopping drug infusion, the infusion may be restarted at 50% of the original infusion rate (e.g. from 100 mL/hr to 50 mL/hr). Otherwise dosing will be held until symptoms resolve and the subject should be premedicated for the next scheduled dose. Subjects who develop Grade 2 toxicity despite adequate premedication should be permanently discontinued from further trial treatment administration.	Subject may be premedicated 1.5h (\pm 30 minutes) prior to infusion of MK-3475 with: Diphenhydramine 50 mg po (or equivalent dose of antihistamine). Acetaminophen 500-1000 mg po (or equivalent dose of antipyretic).
Grades 3 or 4 Grade 3: Prolonged (i.e., not rapidly responsive to symptomatic medication and/or brief interruption of infusion); recurrence of symptoms following initial improvement; hospitalization indicated for other clinical sequelae (e.g., renal impairment, pulmonary infiltrates) Grade 4: Life-threatening; pressor or ventilatory support indicated	Stop Infusion. Additional appropriate medical therapy may include but is not limited to: IV fluids Antihistamines NSAIDS Acetaminophen Narcotics Oxygen Pressors Corticosteroids Epinephrine Increase monitoring of vital signs as medically indicated until the subject is deemed medically stable in the opinion of the investigator. Hospitalization may be indicated. Subject is permanently discontinued from further trial treatment administration	No subsequent dosing
Appropriate resuscitation equipment should be available in the room and a physician readily available during the period of drug administration. For Further information, please refer to the Common Terminology Criteria for Adverse Events v4.0 (CTCAE) at http://ctep.cancer.gov		

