5.1.5.3 Dose Modification

Adverse events (both non-serious and serious) associated with pembrolizumab exposure may represent an immunologic etiology. These adverse events may occur shortly after the first dose or several months after the last dose of treatment. MK-3475 will be withheld for MK-3475-related toxicities and severe or life-threatening AEs as per Table 5. See Section 5.6.1 and Events of Clinical Interest Guidance Document for supportive care, including use of corticosteroids.

Table 5: Dose modification guidelines for MK-3475 related adverse events.

Toxicity	Hold Treatment For Grade	Timing for Restarting Treatment	Treatment Discontinuation
Diarrhea/Colitis	2-3	Toxicity resolves to Grade 0-1	Toxicity does not resolve within 12 weeks of last dose or inability to reduce corticosteroid to 10 mg or less of prednisone or equivalent per day within 12 weeks
	4	Permanently discontinue	Permanently discontinue
AST, ALT, or Increased Bilirubin	2	Toxicity resolves to Grade 0-1	Toxicity does not resolve within 12 weeks of last dose
	3-4	Permanently discontinue (see exception below) ^a	Permanently discontinue
Type 1 diabetes mellitus (if new onset) or Hyperglycemia	T1DM or 3-4	Hold pembrolizumab for new onset Type 1 diabetes mellitus or Grade 3-4 hyperglycemia associated with evidence of beta cell failure	Resume pembrolizumab when patients are clinically and metabolically stable
Hypophysitis	2-4	Toxicity resolves to Grade 0-1. Therapy with pembrolizumab can be continued while endocrine replacement therapy is instituted	Toxicity does not resolve within 12 weeks of last dose or inability to reduce corticosteroid to 10 mg or less of prednisone or equivalent per day within 12 weeks
Hyperthyroidism	3	Toxicity resolves to Grade 0-1	Toxicity does not resolve within 12 weeks of last dose or inability to reduce corticosteroid to 10 mg or less of prednisone or equivalent per day within 12 weeks
	4	Permanently discontinue	Permanently discontinue
Hypothyroidism		Therapy with pembrolizumab	Therapy with pembrolizumab can be continued

Toxicity	Hold Treatment For Grade	Timing for Restarting Treatment	Treatment Discontinuation
Infusion Reaction		can be continued while thyroid replacement therapy is instituted	while thyroid replacement therapy is instituted
	2 ^b	Toxicity resolves to Grade 0-1	Permanently discontinue if toxicity develops despite adequate premedication
	3-4	Permanently discontinue	Permanently discontinue

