Each of the events above is described within this guidance document, along with site requirements for reporting these events to the Sponsor. The information collected should be entered into the narrative field(s) of the Adverse Event module in the database (please note, if narrative entry into the database is not available, please use the narrative text box on the 1727/AER Form). If additional Medical History or Concomitant Medications are reported, the Medical History and Concomitant Medication modules in the database must be updated.

In addition, the guidelines include recommendations on the management of these ECIs. These guidelines are intended to be applied when the physician determines the events to be related to pembrolizumab. Note: if after the evaluation the event is determined not to be related, the physician is instructed to follow the ECI reporting guidance but does not need to follow the treatment guidance (below). Therefore, these recommendations should be seen as guidelines and the treating physician should exercise individual clinical judgment based on the patient. For any question of dose modification or other treatment options, the specific language in the protocol should be followed. Any questions pertaining to the collection of this information or management of ECIs should be directed to your local Sponsor contact.

Dose Modification/Discontinuation

The treatment guidance provides specific direction when to hold and/or discontinue pembrolizumab for each immune related adverse event. Of note, when the guidance states to "discontinue" pembrolizumab this is the permanent discontinuation of treatment with pembrolizumab. "Hold" means to stop treating with pembrolizumab but resumption of treatment may be considered assuming the patient meets the criteria for resumption of treatment.

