3.2 Colitis

The following AE terms, if considered \geq Grade 2 or resulting in dose modification or use of systemic steroids to treat the AE, are considered ECIs and should be reported to the Sponsor within 24 hours of the event:

- Colitis
- Colitis microscopic
- Enterocolitis
- Enterocolitis hemorrhagic
- Gastrointestinal perforation
- Intestinal obstruction
- Necrotizing colitis
- Diarrhea

All attempts should be made to rule out other causes such as metastatic disease, bacterial or parasitic infection, viral gastroenteritis, or the first manifestation of an inflammatory bowel

Final 18-Dec-2014

1

Version 5.0

disease by examination for stool leukocytes, stool cultures, a Clostridium difficile titer and endoscopy. However the AE should be reported regardless of etiology.

Course of Action

Grade 2 Diarrhea/Colitis (4-6 stools/day over baseline, dehydration requiring IV fluids < 24 hours, abdominal pain, mucus or blood in stool):

- Report as ECI
- Hold pembrolizumab.
- Symptomatic Treatment
- For Grade 2 diarrhea that persists for greater than 3 days, and for diarrhea with blood and/or mucus,
 - o Consider GI consultation and endoscopy to confirm or rule out colitis
 - o Administer oral corticosteroids (prednisone 1-2 mg/kg QD or equivalent)
 - When symptoms improve to Grade 1 or less, steroid taper should be started and continued over no less than 4 weeks.
 - Permanently discontinue for inability to reduce corticosteroid dose to 10 mg or less of prednisone or equivalent per day within 12 weeks.
 - If symptoms worsen or persist > 3 days treat as Grade 3

Grade 3 Diarrhea/Colitis (or Grade 2 diarrhea that persists for > 1 week):

- Report as ECI
- Hold pembrolizumab.
- Rule out bowel perforation. Imaging with plain films or CT can be useful.
- Recommend consultation with Gastroenterologist and confirmation biopsy with endoscopy.
- Treat with intravenous steroids (methylprednisolone 125 mg) followed by high dose oral steroids (prednisone 1 to 2 mg/kg once per day or dexamethasone 4 mg every 4 hours) When symptoms improve to Grade 1 or less, steroid taper should be started and continued over no less than 4 weeks. Taper over 6 to 8 weeks in patients with diffuse and severe ulceration and/or bleeding.
- Permanently discontinue for inability to reduce corticosteroid dose to 10 mg or less of prednisone or equivalent per day within 12 weeks.

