- If IV steroids followed by high dose oral steroids does not reduce initial symptoms within 48 to 72 hours, consider treatment with additional anti-inflammatory measures as described in the literature [5]. Discontinue additional anti-inflammatory measures upon symptom relief and initiate a prolonged steroid taper over 45 to 60 days. If symptoms worsen during steroid reduction, initiate a retapering of steroids starting at a higher dose of 80 or 100 mg followed by a more prolonged taper and administer additional anti-inflammatory measures as needed.

Grade 4 events:

Final 18-Dec-2014

Version 5.0

1

- Report as ECI
- Permanently discontinue pembrolizumab.
- Manage as per Grade 3.

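### Section 5.6.1 ties IV steroids for Grade 3 or 4 diarrhea/colitis to more than 1 week of persistence, while the appended guidance sets no wait and Grade 2 gets oral steroids after more than 3 days

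*Combined protocol and SAP*

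**What the plan says.** Section 5.6.1 of the protocol (Diarrhea/Colitis) has two steroid steps. At Grade 2 the wording is "that persists greater than 3 days, administer oral corticosteroids". At Grade 3 or 4 it is "that persists > 1 week, treat with intravenous steroids followed by high dose oral steroids". The section describes its measures as suggestions and applies them once the investigator judges the event related to pembrolizumab.

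The appended Event of Clinical Interest guidance (Appendix 12.9, guidance Section 3.2 Colitis) covers the same event. Its Grade 3 heading adds in parentheses "or Grade 2 diarrhea that persists for > 1 week", and the steroid instruction under that heading is "Treat with intravenous steroids (methylprednisolone 125 mg) followed by high dose oral steroids". For Grade 4 it says "Manage as per Grade 3".

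Two statements connect the texts. Section 5.1.5.3 tells the reader: "See Section 5.6.1 and Events of Clinical Interest Guidance Document for supportive care, including use of corticosteroids". The guidance overview (Section 1) says: "For any question of dose modification or other treatment options, the specific language in the protocol should be followed".

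**The concern.** The two texts give different steroid triggers for the same event at the same grade, and the protocol text has the later one. Within Section 5.6.1 the order also runs the wrong way, because the milder grade reaches its first steroid step sooner than the severe and life-threatening grades. Section 12.8 describes Grade 4 as life-threatening and calling for urgent intervention, which does not fit a trigger of more than a week.

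What is at stake is the management of severe immune-related colitis, in a combination where Section 5.6.1 itself notes that both drugs can cause diarrhea and asks sites to watch for bowel perforation. An investigator who follows the protocol literally has no steroid instruction for Grade 3 or 4 during the first week.

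There is a secondary link to the dose-limiting toxicity definition. Section 5.3, item 3, counts Grade 3 non-hematologic toxicity that lasts more than 3 days despite optimal supportive care. A pembrolizumab-related Grade 3 event could meet that definition before Section 5.6.1's own steroid step applies. No effect on the operating characteristics of the dose-finding rule is claimed.

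**Working it through.** No sample size, power or error rate is involved, so the check is a comparison of texts.

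**Step 1. Stated steroid triggers, side by side**

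| Grade | Protocol Section 5.6.1 | Appended guidance Section 3.2 |
|---|---|---|
| 2 | Oral, after more than 3 days | Oral, after more than 3 days, or with blood and/or mucus |
| 3 | IV then high-dose oral, after more than 1 week | IV then high-dose oral, no wait |
| 4 | As Grade 3, after more than 1 week | As Grade 3, no wait |

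**Step 2. Where the one-week condition belongs.** In guidance 3.2 the words "or Grade 2 diarrhea that persists for > 1 week" are a second route into Grade 3 management for a Grade 2 event. They do not qualify Grade 3. Section 5.6.1 attaches the same duration to Grade 3 or 4 instead.

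**Step 3. Size of the differences, in days**
- Between texts, Grade 3 or 4: 7 − 0 = 7.
- Within Section 5.6.1, Grade 3 or 4 against Grade 2: 7 − 3 = 4. This compares an IV step with an oral one, so it shows the order of the triggers and is not a like-for-like delay.

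**Step 4. Is a persistence condition normal in Section 5.6.1?** Six events there carry a Grade 3-4 steroid instruction: pneumonitis, diarrhea/colitis, hypophysitis, hyperthyroidism, hepatic events, and renal failure or nephritis. Infusion reactions (Table 7) are left out because corticosteroids are only one option there. Diarrhea/colitis is the only 1 of the 6 with a persistence condition. For pneumonitis the text says "immediately treat with intravenous steroids".

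**Step 5. Does anything resolve the conflict?** Section 5.1.5.3 points to both texts without ranking them. The only ranking is in the guidance overview, which defers to the protocol on treatment options. On that reading the more-than-1-week trigger governs.

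**The case against.** The strongest case on the other side has four parts.

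- **The text does not withhold steroids.** Section 5.6.1 leaves care to the treating investigator, and Section 5.5.2 allows systemic glucocorticoids for a suspected immunologic event with no minimum duration. The sentence just before the guidance's deference to the protocol calls for individual clinical judgment. A patient who reaches Grade 3 after more than 3 days at Grade 2 has already met the oral trigger. All of this stands and limits the harm. A patient who presents at Grade 3 or 4 still has no steroid step until after a week.
- **Other protections apply.** Table 5 holds MK-3475 at Grade 2-3 and stops it at Grade 4. Section 5.4 holds both drugs for enterocolitis of Grade 2 or higher. Section 5.6.1 advises aggressive anti-diarrheals and considering endoscopy from Grade 2. This stands too, but none of it replaces the steroid instruction.
- **Afatinib commonly causes diarrhea, so a trial of anti-diarrheals first is reasonable, and the other five events are not fair comparators.** The overlap is real. It does not explain the wait, because Section 5.6.1 applies once the event is judged pembrolizumab-related, and the overlap cannot justify an earlier trigger at Grade 2 than at Grade 3 or 4. No rationale is given.
- **Removing the condition would not fully align the texts.** Correct. Guidance 3.2 also starts oral steroids for diarrhea with blood and/or mucus, and it treats Grade 2 symptoms that worsen or last more than 3 days as Grade 3. These remaining differences are separate from the Grade 3 or 4 conflict.

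**Conclusion.** The concern holds. At Grade 3 or 4 the protocol states a trigger of more than 7 days for IV steroids where its own appendix states no wait, and within Section 5.6.1 the more severe grades have the later first steroid step. The correction should be made, because the text concerns the management of severe or life-threatening events.

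The conclusion rests on two readings. The first is that the guidance's one-week condition qualifies Grade 2 only, which its heading makes plain. The second is that the guidance's deference to the protocol covers steroid timing as a treatment option. If the second reading is disputed, investigators still face two conflicting instructions with no ranking.

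The documents do not show that any patient would be treated late, and they contain no outcome data on steroid timing. No endpoint, analysis or stated statistical figure changes.

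**What to change.** In Section 5.6.1, remove the persistence condition from the Grade 3 or 4 line and attach it to Grade 2, as guidance 3.2 does. Possible wording: *Grade 3 or 4 diarrhea/colitis with no minimum duration, and Grade 2 diarrhea lasting beyond 1 week: give IV steroids, then high-dose oral steroids.* Keep the Grade 2 oral step after more than 3 days.

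If the wait is deliberate, for example to try anti-diarrheals first because afatinib can cause the same event, state that reason in Section 5.6.1 and amend guidance 3.2 to match.

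While the text is open, the sponsor could also decide whether to carry over the two remaining Grade 2 provisions of guidance 3.2 (blood and/or mucus; worsening or persistence beyond 3 days).

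The cost is one line of protocol wording plus clinical sign-off by the sponsor and the drug suppliers.
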